7.3 Serious Adverse Events

A serious adverse event (SAE) is any AE occurring at any dose that results in any of the following outcomes: death, a life-threatening AE, inpatient hospitalization or prolongation of existing hospitalization, a persistent or significant disability/incapacity, or a congenital anomaly/birth defect. While an unanticipated adverse device effect (UADE) is any device-related SAE that meets one or more of the criteria listed in the Sec. 9.1.3 of the Protocol in page 49.

An overall summary of frequency count and the binomial incidence rate with associated 95% CIs will be presented to describe the incidents of treatment emergent SAEs. Note that 95% CIs presented are for the overall summary analyses of SAE, but not for the by-visit analyses. Percentages and corresponding 95% CIs will be displayed to 1 decimal place.

The incidence of all treatment-emergent SAEs by SOC and PT within SOC will be presented for the following categories:

- Any SAE
- Any SAE related to BELKYRA
- Any SAE related to VOLUMA
- Any SAE related to anesthesia
- Any SAE related to study procedure

- Any SAE related to BELKYRA/VOLUMA treatment and leading to discontinuation of treatment
- Any SAE by maximum severity

7.4 Other Safety Analysis

Injection Site Reactions (ISR) following treatment with dermal fillers (VOLUMA) will be analyzed using the AE terms captured in the patient diary (i.e. ISR Diary).

ISR events will be tabulated by PT and sorted by descending frequency. If a subject has multiple occurrences (start and stop) of an event associated with a specific SOC and PT, a patient will only be counted once in the incidence count. The total number of events will also be presented.

An overall summary of frequency count and the binomial incidence rate with its associated 95% CIs will be presented to describe ISRs.

The 95% CIs for the binominal incidence rate will be calculated using the Clopper and Pearson exact method.

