7.1.8 Injection Site Reaction (ISR) Diary

The ISR Diary will be completed by the subject beginning on the day of treatment with VOLUMA™ and for daily for 4 weeks.

If Touch-up treatment is received at Visit 5, the initial ISR Diary provided at Visit 4 will be collected. A new ISR Diary will be dispensed and started at touch-up treatment. Four weeks of ISR will be collected after the last VOLUMA™ treatment. An example of the ISR Diary is available in *Appendix 11*.

Clinical Study Protocol: CMO-MA-FAS-0513

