9.1.1.3 Injection Site Reaction (ISR)

ISRs following treatment with dermal fillers include redness, pain after injection, tenderness to touch, firmness, swelling, lumps/bumps, bruising, itching, discoloration, and other specified events. Subjects will maintain a diary record of the presence, location, frequency, severity, and duration of any ISR for 4 weeks after treatment with VOLUMA™ (initial treatment at Visit 4 and Touch-up at Visit 5, if applicable). (See *Section 7.1.8: Injection Site Reaction (ISR) Diary* for further details).

Subjects will indicate the occurrence of an ISR and severity (none, mild, moderate, severe) of the event. ISRs that persist longer than 4 weeks (i.e., ongoing at the end of the diary period) will be reported as AEs and followed as described in *Section 9.2: Procedure for Reporting Adverse Events*. If an ISR is ongoing or appears 4 weeks after the subject’s last study visit, it will be followed up by Allergan Product Surveillance separate from this study protocol.

Clinical Study Protocol: CMO-MA-FAS-0513

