9.1.4 Severity

Definitions for classification of severity appear below in Table 9.1. The Investigator will review these definitions with the subject for use when completing the subject diary. For events reported on the AE eCRF, e.g., ISRs that persist beyond the diary period and other AEs, the Investigator will determine the severity classification based on these definitions, his/her experience in the use of dermal fillers, and/or the subject's description of the event.

Note: A "severe" AE is not the same as an "SAE", which is defined above. Seriousness of AEs is defined in *Section 9.1.2: Serious Adverse Events (SAE)*.

Clinical Study Protocol: CMO-MA-FAS-0513

Table 9.1 Classification of Adverse Events by Severity

Mild:	Symptoms are barely noticeable or do not make the subject uncomfortable. The AE/ISR does not interfere with performance or functioning. Prescription drugs are not ordinarily needed for relief of symptoms.
Moderate:	Symptom are of sufficient severity to make the subject uncomfortable. Performance of daily activities is influenced. Treatment of symptom(s) with prescription drugs/therapies may be needed.
Severe:	Symptoms are of such sufficient severity to cause the subject severe discomfort. Performance of daily activities is compromised. Treatment of symptom(s) with prescription drugs/therapies may be needed.
Not applicable:	In some cases, an AE/ISR may be an “all or nothing” finding that cannot be graded.

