7.6 Subgroup Analyses for Safety Variables

Not applicable.

8. Pharmacokinetic, Biomarker, Genomic, or Immunogenicity Data Analyses

Not applicable.

9. Health Outcomes Data Analyses

There are no health outcomes analyses planned for this study.

10. Interim Analyses

There is no interim analysis planned for this study.

11. Data Collected but not Analyzed

Not Applicable.

12. References

[REDACTED]

Allergan's Study Protocol

Study Number

CMO-MA-FAS-0513

Study Title

A Prospective, Open-label Study to Evaluate Sequential Treatment with BELKYRA[®] and Juvéderm[®] VOLUMA[™] with Lidocaine for Overall Improvement in Jawline Contour

13. **Appendices**

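### SAP 7.4 summarises diary injection site reactions without severity or duration, so severe non-serious reactions of up to 4 weeks are not routinely shown by severity

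*SAP*

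**What the plan says.** **Collected.** Protocol 9.1.1.3: "Subjects will maintain a diary record of the presence, location, frequency, severity, and duration of any ISR for 4 weeks after treatment with VOLUMA™". It also states: "Subjects will indicate the occurrence of an ISR and severity (none, mild, moderate, severe) of the event". Protocol 6.3.3 asks for one diary page per day, and protocol 9.1.4 has the investigator go through the severity definitions with the subject for diary use.

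**Planned.** SAP 7.4: "ISR events will be tabulated by PT and sorted by descending frequency". For a repeated event, "a patient will only be counted once in the incidence count". The section adds the total number of events and an overall incidence with Clopper-Pearson 95% CI. It mentions neither severity nor duration, and no part of it is blacked out. SAP section 11, "Data Collected but not Analyzed", is answered as not applicable.

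**Route to the adverse event tables.** Protocol 9.1.1.3: "ISRs that persist longer than 4 weeks (i.e., ongoing at the end of the diary period) will be reported as AEs". Protocol 9.1.4 describes the same route: "For events reported on the AE eCRF, e.g., ISRs that persist beyond the diary period and other AEs". The SAP specifies maximum-severity tables in 7.2 (treatment-emergent AEs) and 7.3 (SAEs) only.

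**Touch-up.** Under protocol 7.1.8, when a touch-up is given at Visit 5, "the initial ISR Diary provided at Visit 4 will be collected" and a new four-week diary is started. Neither document says how a reaction recorded in both diaries is to be joined.

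**The concern.** Severity and duration are the informative part of a filler reaction diary. A count by term puts a mild bruise of one day in the same cell as a severe swelling of three weeks. Protocol 1.2 names safety as well as effectiveness as a reason for the study, and the diary is its most detailed record of local tolerability after VOLUMA. As specified, the ISR output can say how many subjects had swelling. It cannot say how many had severe swelling, or for how long.

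The touch-up adds a smaller problem. Changing diaries at Visit 5 leaves open whether a continuing reaction is one event or two, and how its length is measured. It also affects how the protocol's 4-week reporting rule reads.

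**Working it through.** The documents state no figure on this point, so there is none to reproduce. The check is a comparison of sections, followed by simple arithmetic.

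**1. Follow one reaction through the plan.** Take a severe, non-serious swelling that starts on the day of the first VOLUMA injection and lasts 21 days, with no touch-up.
- Diary (protocol 7.1.8, 9.1.1.3): recorded daily, graded severe, duration 21 days.
- SAP 7.4: adds one subject and one event under its term. Grade and duration are not used.
- AE eCRF (protocol 9.1.1.3, 9.1.4): 21 < 28 days and not ongoing when the diary ends, so the stated rule does not send it there.
- SAP 7.2 severity table: fed from AEs, so not reached by that rule.
- SAP 7.3 severity table: not serious, so not reached.

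**2. What the missing row would show.** Assumption: 40 subjects receive VOLUMA. Protocol 10.7 plans on 40 after 20% loss from 50. Exact limits for x of n: lower = Beta(0.025; x, n−x+1), upper = Beta(0.975; x+1, n−x). For x = 0 the upper limit is 1 − 0.025^(1/40) = 0.088.

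| Subjects with a severe ISR | Rate | Exact 95% CI |
|---|---|---|
| 0/40 | 0% | 0 to 8.8% |
| 4/40 | 10% | 2.8 to 23.7% |
| 8/40 | 20% | 9.1 to 35.6% |

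These counts are illustrations; the documents give no ISR rates.

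**3. Diary windows.** Visit 5 is 14 days after Visit 4 (protocol 3.3), and the diary runs 28 days after the last VOLUMA treatment (protocol 7.1.8).
- No touch-up: the diary ends at day 28.
- Touch-up: 14 + 28 = 42, so the second diary ends at about day 42.

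**4. Event totals.** Let t be the share of subjects with a touch-up and s the share of their reactions that span Visit 5. If every such reaction were entered as two events, and reactions were spread evenly over subjects, the event total would rise by the factor 1 + t·s. Neither t nor s is in the documents. Assuming t = 0.2 to 0.8 and s = 0.1 to 0.5 gives 1 + 0.2 × 0.1 = 1.02 up to 1 + 0.8 × 0.5 = 1.40. Subject-level incidence does not move, because each subject counts once per term. Maximum severity per subject and term does not move either.

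**5. The 4-week rule.** Take a reaction that starts at the first injection and lasts 29 to 41 days.
- No touch-up: longer than 28 days, and ongoing at day 28. Both halves of the rule are met.
- Touch-up: still longer than 28 days, but over before day 42. The first half is met and the second is not.

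Protocol 9.1.1.3 presents the two halves as equivalent. After a touch-up they need not be.

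**The case against.** The best defence is that no commitment is broken. Protocol 10.5.5 promises severity summaries for treatment-emergent AEs, not for diary ISRs; none of the visible objectives concerns safety; and the study is a descriptive, single-arm Phase IV trial of about 50 subjects. That is true, and it limits the point to an improvement. It does not explain why severity and duration are collected daily, left out of SAP 7.4, and not listed in SAP section 11.

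Some material cannot be seen: the visit procedures between protocol 6.1.4 and 6.3.3 are blacked out, the diary form (Appendix 11) is not shown, and the table shells mentioned in SAP 3.1 are not in the documents. A severity shell or a diary reconciliation step may exist. The point therefore concerns the SAP text.

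Three stronger readings are tempting, and the documents do not support them.
- *Severe short reactions can reach no severity table.* An investigator who asks about AEs at each visit (protocol 9.1.1.1) could also enter such a reaction as an AE, and one meeting the SAE criteria would enter the SAE table. The plan does not route them there routinely; it does not bar them.
- *Every reaction present at Visit 5 counts twice.* SAP 7.4 describes multiple occurrences in terms of starting and stopping, under which an unbroken reaction could be a single event. Double counting is possible only because no linking rule is given.
- *The AE rule is applied differently to touch-up subjects.* A reaction of 29 to 41 days meets the duration half of the rule with or without a touch-up. The text is ambiguous there; it does not prescribe different handling.

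**Conclusion.** The point holds as a minor but useful one. Severity and duration of diary ISRs are collected, yet SAP 7.4 plans no summary of either, and SAP section 11 does not acknowledge this. As a result, severe non-serious reactions of up to 4 weeks are not routinely included in any severity table specified in the SAP text. How many subjects this concerns is unknown. At the assumed 40 treated subjects, even a finding of no severe ISR would be worth reporting (upper limit 8.8%).

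The touch-up issue is secondary. It can affect event totals (factor 1.02 to 1.40 under the assumed ranges, if spanning reactions are split) and durations. It also exposes an ambiguity in the protocol's reporting rule. It does not affect subject-level incidence or its CI.

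**What to change.** In SAP 7.4, before database lock:

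1. Tabulate each ISR term by maximum severity per subject (mild, moderate, severe), with number, percentage and exact 95% CI.
2. Tabulate each ISR term by duration class in the same way. The visit schedule suggests cuts at 14 and 28 days; any finer classes should be fixed before lock.
3. For touch-up subjects, state that a reaction recorded without interruption on both sides of Visit 5 is one event for event totals and duration, and say how a missing diary page is treated. Flag these events: where the same site is re-injected, a lingering reaction cannot be told from a new one, so the joined duration may be too long.
4. Correct SAP section 11 if any diary item remains unanalysed.

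Separately, reconcile the two halves of the ISR reporting rule in protocol 9.1.1.3 with the diary restart in 7.1.8. This belongs in the protocol, because entering an ISR as an AE is an investigator and eCRF step that the SAP cannot perform afterwards.

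The SAP part costs two extra tables and one derivation on data already collected, with no new visits or assessments. The protocol clarification is a change of wording, though it may alter which reactions are entered as AEs.

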7.5 Pregnancy

All positive results of pregnancy tests will be listed.

7.6 Subgroup Analyses for Safety Variables

Not applicable.

8. Pharmacokinetic, Biomarker, Genomic, or Immunogenicity Data Analyses

Not applicable.

9. Health Outcomes Data Analyses

There are no health outcomes analyses planned for this study.

10. Interim Analyses

There is no interim analysis planned for this study.

11. Data Collected but not Analyzed

Not Applicable.

12. References

[REDACTED]

Allergan's Study Protocol

Study Number

CMO-MA-FAS-0513

Study Title

A Prospective, Open-label Study to Evaluate Sequential Treatment with BELKYRA[®] and Juvéderm[®] VOLUMA[™] with Lidocaine for Overall Improvement in Jawline Contour

13. **Appendices**
